**Table 5 PCS Criteria for Vital Signs (Continued)**

	Normal Range (mm Hg)	PCS High (mm Hg)	PCS Low (mm Hg)
Systolic blood pressure, supine	7-9 years: 80-115 10-12 years: 85-120 13-17 years: 90-130 $\geq$ 18 years: 110-140	$\geq$ 140 and increase $\geq$ 20 $\geq$ 140 and increase $\geq$ 20 $\geq$ 140 and increase $\geq$ 20 $\geq$ 180 and increase $\geq$ 20	$\leq$ 90 and decrease $\geq$ 20
Diastolic blood pressure, supine	7-9 years: 40-75 10-12 years: 40-80 13-17 years: 40-80 $\geq$ 18 years: 51-85	$\geq$ 90 and increase $\geq$ 15 $\geq$ 90 and increase $\geq$ 15 $\geq$ 90 and increase $\geq$ 15 $\geq$ 105 and increase $\geq$ 15	$\leq$ 50 and decrease $\geq$ 15

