9.4.3 Vital Signs

Blood pressure (BP) and pulse rate will be measured using a standard digital meter after the patient has rested for at least 5 minutes in a supine position.

The patient must then be instructed to change from a supine to a standing position in a manner that includes passing through a sitting position before assuming an upright position. Blood pressure and pulse rate will be measured after the patient has been standing for at least 1 minute but no longer than 5 minutes.

Vital signs should be assessed prior to blood sampling.

Abnormalities of clinical significance must be recorded as an adverse event on an *Adverse Event Form*.

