## 12.2 General Methodology for Other Safety Data

Unless otherwise specified, tables, graphs, and listings will be based on the APTS, and the tables will be presented for all patients and by lead-in study and by lead-in treatment.

The denominators for the summaries of a given variable will be based on the number of patients with non-missing values at a given visit or during the assessment period.

Descriptive statistics for the safety variables, both absolute values and change from baselines (baseline at randomisation in lead-in study and OLEXA), will be presented by visit and for the last assessment. All available post-OLEXA assessments will be included in the identification of the last assessment.

The number and percentage of patients with at least one PCS value at any post-baseline assessment time point will be summarized by variable. All available assessments will be included in the evaluation of PCS values.

The number and percentage of patients with values out-of-reference range and/or PCS range will be summarized by variable, visit, and last post-baseline assessment.

For patients with post-baseline PCS values, listings will be provided including all the values for those patients for the variable, with flagging of PCS values and out-of-reference-range values.

The PCS definition will be provided by H. Lundbeck and are stated in [Appendix IV](#).

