**Table 4 PCS Criteria for Vital Signs, Weight/BMI, and Waist Circumference**

Parameter	CDISC Term	Unit	PCS LOW	PCS HIGH
Waist circumference	WSTCIR	Cm	decrease $\geq$ 7%	increase $\geq$ 7%
Weight	WEIGHT	Kg	decrease $\geq$ 7%	increase $\geq$ 7%
Body Mass Index	BMI	kg/m 	decrease $\geq$ 7%	increase $\geq$ 7%
Pulse rate, supine/sitting/unknown	PULSE	beats/min	< 50 and decrease $\geq$ 15 $\geq$ 15	$\geq$ 120 and increase $\geq$ 15
Diastolic blood pressure, supine/sitting/unknown	DIABP	mmHg	$\leq$ 50 and decrease $\geq$ 15	$\geq$ 105 and increase $\geq$ 15
Systolic blood pressure, supine/sitting/unknown	SYSBP	mmHg	$\leq$ 90 and decrease $\geq$ 20	$\geq$ 180 and increase $\geq$ 20
Orthostatic systolic blood pressure a	OBP	mmHg	$\leq$ -30	
Orthostatic pulse rate a	OPR	beats/min		$\geq$ 20
Temperature b	TEMP	°C	decrease $\geq$ 2	$\geq$ 38.3 and increase $\geq$ 2

Increase/decrease is relative to the baseline value

aFor definition of orthostatic blood pressure and pulse rate, see text after Table 3

bNote, the diurnal variation may affect the temperature. Morning temperature is lower

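### Under 18, a blood-pressure fall that ends inside the SAP's own normal range can be counted as PCS Low. Separately, the ±7% weight/BMI rule has no growth-standardised companion.

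*SAP*

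**What the plan says.** **Blood-pressure limits.** Table 5 gives normal ranges by age. For supine SBP they are "7-9 years: 80-115 10-12 years: 85-120 13-17 years: 90-130", and 110-140 at 18 and over. For supine DBP they are "7-9 years: 40-75 10-12 years: 40-80 13-17 years: 40-80", and 51-85 at 18 and over. PCS High is also banded: 140/90 under 18 and 180/105 from 18, with a rise of at least 20/15 mmHg. PCS Low has a single entry per parameter: SBP ≤90 with a fall of at least 20, and DBP ≤50 with a fall of at least 15. Both parts must be met.

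**Table 4.** "Table 4 PCS Criteria for Vital Signs, Weight/BMI, and Waist Circumference" carries the same PCS Low limits. Its PCS High limits (180/105) have no age restriction, and its rows cover supine readings, for example "Diastolic blood pressure, supine/sitting/unknown". Protocol 9.4.3 takes blood pressure "after the patient has rested for at least 5 minutes in a supine position", so both tables apply to these readings. Table 5 is titled a continuation of Table 4; no text says which governs.

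**Weight and BMI.** Table 4 flags a change of 7% or more from baseline in either direction.

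**Reporting.** SAP 12.2 plans the headline count: "The number and percentage of patients with at least one PCS value at any post-baseline assessment time point will be summarized by variable". It also plans: "The number and percentage of patients with values out-of-reference range and/or PCS range will be summarized by variable, visit, and last post-baseline assessment". Listings for patients with PCS values flag PCS and out-of-range values separately. SAP 3.1 places PCS vital signs and weight, relative to OLEXA, in the primary safety endpoint.

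**The concern.** Within Table 5 the two directions behave differently. Every PCS High limit lies outside its band's normal range. PCS Low does so only from age 18, in a study of patients aged 7 to 18. The headline PCS Low count under 18 can therefore combine two different things: falls to a reading below the normal range, and falls that end at a reading the SAP itself calls normal. A reader of the table cannot tell which.

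Weight and BMI raise a related problem. Patients grow over 26 weeks, there is no control arm, and neither document provides an age- and sex-standardised measure. An increase flag mixes expected growth with any drug effect.

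At stake is how the primary safety tables can be read. Protocol 17.10.1 answers the primary objective by clinical judgement of the safety results as a whole, so what the counts mean matters even though nothing is tested.

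**Working it through.** **1. Distance of each limit from the normal range (inputs: Table 5, mmHg).**

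PCS High minus upper normal limit:
- SBP: 140−115 = 25; 140−120 = 20; 140−130 = 10; at ≥18 y, 180−140 = 40.
- DBP: 90−75 = 15; 90−80 = 10; 90−80 = 10; at ≥18 y, 105−85 = 20.

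All lie outside the range. PCS Low minus lower normal limit (positive means inside the range):
- SBP: 90−80 = +10; 90−85 = +5; 90−90 = 0; at ≥18 y, 90−110 = −20.
- DBP: 50−40 = +10 in each of the three bands under 18; at ≥18 y, 50−51 = −1.

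**2. Does the overlap survive the fall condition?** Take every whole-mmHg pair (baseline, later) with both values inside the normal range, and count those meeting both parts of PCS Low.

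| Parameter, age | In-range values at or below the limit | Pairs meeting both parts |
|---|---|---|
| DBP 7-9 | 40-50 | 176 of 36² = 1296 |
| DBP 10-12 | 40-50 | 231 of 41² = 1681 |
| DBP 13-17 | 40-50 | 231 of 1681 |
| SBP 7-9 | 80-90 | 121 of 1296 |
| SBP 10-12 | 85-90 | 81 of 1296 |
| SBP 13-17 | 90 only | 21 of 1681 |
| SBP or DBP ≥18 | none | 0 |

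These counts show that the overlap exists; they are not expected rates. Example: at age 8, DBP 65 then 48 is inside 40-75 both times, falls by 17, and is PCS Low. Counter-example: DBP 50 then 45 falls by only 5 and is not.

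**3. Illustrative size for DBP.** The documents give no blood-pressure mean, SD or correlation, so these are assumed. Readings are normal, rounded to 1 mmHg, with equal within-patient correlation r, no drug effect, a baseline and seven later visits (Weeks 1, 2, 4, 8, 12, 18, 26, from the flow chart), and at least 400,000 simulated patients per cell. Scenario A uses the mid-range as mean and range/3.92 as SD. Scenario B uses a higher mean and a smaller SD.

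| Age, scenario (mean, SD) | Flagged at least once, r = 0.4 / 0.6 / 0.8 | Share of flagged with no flagged value below 40 |
|---|---|---|
| 7-9, A (57.5, 8.9) | 20.4 / 10.4 / 1.7% | 73-76% |
| 7-9, B (60, 8) | 12.3 / 5.4 / 0.6% | 87-88% |
| 10-17, A (60, 10.2) | 23.5 / 13.3 / 3.2% | 72-74% |
| 10-17, B (65, 8) | 6.2 / 2.7 / 0.3% | 94-95% |

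The rate moves widely with the assumptions. The share stays high throughout.

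**4. Weight and BMI increase rule.** Let g be assumed weight growth (%/year), h height growth (%/year) and s the SD of the 26-week change (percentage points).
- Weight: P(≥7%) = 1 − Φ((7 − g/2)/s). With g = 0, s = 3 this is 1 − Φ(2.33) = 1.0%. With g = 15, s = 3 it is 1 − Φ(−0.17) = 56.6%.
- BMI: mean change = 100 × [(1 + g/200)/(1 + h/200)² − 1]. With g = 0, h = 5 the mean is −4.8% and P is about 0% (s = 3). With g = 15, h = 4 the mean is 3.3% and P is 11-23% (s = 3-5). With g = 15, h = 0 the mean is 7.5% and P is 57% (s = 3).

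Over g = 0-15, h = 0-5 and s = 3-5, the range is about 1-57% for weight and 0-57% for BMI.

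**The case against.** **The rule may be deliberate.** A level-plus-fall rule can be meant to catch a large drop that ends in range, and SAP 12.2 treats PCS and out-of-range as separate attributes. This stands, and it is why the rule should be kept. It does not make the headline count separable.

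**The listings already show it.** An in-range PCS value would carry one flag and not the other. That is true patient by patient, if Table 5's ranges are the reference. They are the only blood-pressure ranges in the documents, but SAP 12.2 does not name them, and its and/or summary is not a promised split of PCS Low.

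**Stronger readings a reader might infer.** One is that any low-normal reading under 18 is PCS. It is not: a child stable at DBP 45 is never flagged. Another is that SBP at 13-17 has the same problem. There the limit equals the lower bound and only a reading of exactly 90 overlaps. A third is that the simulated percentages forecast this trial. They do not; only the mmHg distances come from the documents.

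**Tables 4 and 5 conflict.** Under 18, PCS High is 180/105 in one and 140/90 in the other. The continuation title, the named ages, and a ≥18 row equal to Table 4 make it likely that Table 5 is meant to govern. This is missing wording, not an analysis error.

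**Weight is a request, not a contradiction.** Nothing in the documents contradicts a ±7% rule, and growth does not inflate the decrease side. Protocol 17.10.2 promises further exploratory description of variables strongly dependent on sex and age. But the SAP specifies nothing of the kind for weight, and SAP 17 removes the random-slope model for which the protocol had named weight.

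**Conclusion.** The point holds as a cheap improvement. Under 18, PCS Low reaches 10 mmHg into Table 5's own normal range for DBP at every age and for SBP at 7-9 years, and 5 mmHg for SBP at 10-12 years. At 13-17 years SBP overlaps at one value, and at 18 and over there is no overlap. A reading in the overlap counts only with a fall of at least 20/15 mmHg. These facts come from the SAP alone.

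Under the assumed distributions, 72-95% of under-18s flagged for low DBP had only in-range flagged values. The proportion flagged at all ran from 0.3% to about 24% and should not be quoted as an expectation.

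For weight, growth and variation alone put about 1-57% above +7% under the assumptions shown. BMI is so sensitive to assumed height growth (about 0-57%) that it cannot be relied on to remove the effect.

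It would be tempting to infer that the trial's safety conclusion is compromised. The documents do not support that: the outputs are descriptive, no test depends on them, and the objective is judged clinically on all the safety data.

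**What to change.** 1. Keep the PCS Low rule. State in SAP 12.2 that Table 5's normal ranges are the blood-pressure reference ranges, and say whether the age band is taken at OLEXA or at the visit. Report PCS Low counts split by whether any flagged value lies below the band's lower normal limit. Any change to the limits themselves is for the sponsor to reconcile.
2. Add one sentence saying whether Table 5 governs supine blood pressure under 18.
3. Keep the ±7% rule. Add descriptive age- and sex-standardised (SD-score) summaries of height, weight and BMI at OLEXA, Week 12 and Week 26, naming the growth reference.

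Cost: SAP wording, one extra split in a table, and a growth-reference lookup from sex, age, height and weight already collected. The downside is a little programming. No flag is lost, so sensitivity and comparability with the company's standard criteria are unchanged.
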